In Part C, subjects will enter the research center on Day -2 and remain resident in the research facility to undergo safety, PD, PK and diseases assessments through the morning of Day 2 of Part C, after which they will be discharged home. Subjects will return on an outpatient basis and undergo safety, PK/PD and disease assessments as described in the schedule of assessments. In addition, telephone assessments for safety and disease assessment will be performed on a weekly (during Month 1) and monthly basis (Months 2 through 5) where no clinic visit is scheduled. In such a case that the dose is reduced, the subject should be scheduled for a clinic visit to occur within approximately 2 weeks of the dose reduction. Following completion of the [REDACTED] dosing period, or in the case of early discontinuation from the study, subjects will return 2 and 4 weeks after the final dose for follow-up visits to undergo safety, PK/PD and diseases assessments and end of study procedures. In cases where the subject is unable to return to the clinic due to significant physical or geographic limitations, or at the Investigator's discretion, a nurse may be sent to the subject's home and the study visit procedures performed in the subject's home, except for the day 29 visit which must be done within the research center.

Adverse events will be assessed throughout the study duration in each Part and will be recorded in the case report form when reported.

Study procedures are further described in [Table 1](#) for Part A and [Table 2](#) for Part C and in [Section 6](#).

Duration of Study Participation:

The duration of study involvement for each subject will be up to approximately 36 days for Part A (including up to 30 days for screening), and 169 days for Part C.

PROTOCOL SYNOPSIS (CONTINUED)

Number of Subjects per Group:

Up to [REDACTED] will be enrolled. Subjects who demonstrate a pressor effect in Part A, who complete Part A, and who remain otherwise eligible are eligible to participate in Part C.
[REDACTED]

Study Population:

This study will enroll adult subjects with confirmed nOH due to MSA, PAF, or Parkinson's disease and who meet other inclusion and exclusion criteria defined below.

Inclusion Criteria:

1. Male or female at least 40 years of age.
2. Subject is able to communicate well with the Investigator and understands the expectations of the study.

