- d. The orthostatic standing test will be performed in the morning before eating breakfast at approximately the same time of day each visit under fasting conditions after midnight to avoid the confounding effect of post-prandial hypotension. In addition, at least 4 hours after dosing (but no more than 7 hours) and before lunch, the standing test will be repeated. At each time point, BP and HR measurements will be recorded with automated (or manual) sphygmomanometer while supine at 5 and 10 min (with the torso and head elevated 30 degrees from horizontal), after seated at 5 and 10 min and after 1, 3, 5, and 10 min while standing. The standing time will be measured with a chronometer and the duration of standing will be recorded. More details related to the sequence of dosing and orthostatic assessments are described below. For the Day 155 and 169 assessments, the timing of the "postdose" orthostatic test should be calculated based on the Day 1 dosing time.
- e. On Days 8, 22, 57 and 113, supine blood pressures will be collected twice in the morning before eating (after 5 and 10 minutes resting at 30° elevation), and twice again at least 4 hours after dosing (but no more than 7 hours and before lunch) after 5 and 10 minutes resting at 30° elevation. On Day -2, supine blood pressures should be measured (after 5 and 10 minutes resting at 30° elevation).

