- k. Blood collection for NE analysis will be collected on Day 1 (within 30 minutes before dosing) and upon return to the clinic on Day 29. Please refer to the central laboratory manual.

SCHEDULE OF STUDY ASSESSMENTS (CONTINUED)

- I. Clinician's/Subject's Global Impression and OHQ (OHSA and OHDAS components) to be administered during clinic visits by a trained clinician and recorded on standardized paper forms (See [Appendix 4](#)). In addition while at home, the Clinician's/Subject's Global Impression and OHQ will be completed by telephone with the study coordinator. On all visit days the OHQ and Global Impression assessments should be completed at least 4 hours after dosing (but no more than 7 hours) and before lunch. For the Day 155 and 169 assessments, the timing of the "postdose" questionnaires should be calculated based on the Day 1 dosing time.
- m. On the study visit days marked above, subjects will receive a dose of study medication in the morning after supine blood pressures and the orthostatic standing test has been completed. On non-study visit days the subjects should take their dose of study medication in the morning at approximately the same time of day. On study days where the subject is traveling to the clinic, the subject should take their dose of study medication at home before traveling to the clinic. Subjects will return to the clinic on the day of their final dose. Day 140 is the day of the last dose received at the end of 5 months (20 weeks).
- n. Subjects will complete the Subject Satisfaction Survey on Days -1, 15, 29 and 140 (or at the time of early discontinuation) using the appropriate questionnaire listed in [Appendix 5](#).
- o. Safety labs should be collected Day -2 or on Day -1.

Sequence of study procedures during study visits (with *hypothetical* times for illustration):

- 7:00 am -Wake up
- 7:30 am - supine blood pressure after 5 and 10 minutes resting at 30 degrees elevation and orthostatic standing test (where applicable)
- 8:00 am - Dose with TD-9855 and eat breakfast

After a minimum of 4 hours but no more than 7 hours after dosing and before lunch:

- 12:00 pm - supine blood pressure after 5 and 10 minutes resting at 30 degrees elevation and orthostatic standing test (where applicable)
- 12:30 pm - Clinician/subject impression and OH Questionnaires (OHDAS and OHSA)
- 12:45 pm - lunch

TABLE OF CONTENTS

	PAGE
PROTOCOL SYNOPSIS	2
SCHEDULE OF STUDY ASSESSMENTS	12
LIST OF ABBREVIATIONS AND DEFINITION OF TERMS	20

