In the case where a subject develops the presence or worsening of supine hypertension (as determined by the Investigator with agreement from the Sponsor) or other adverse events suggesting intolerance, the dose can be withheld for 3 days and resumed at a dose level 50% (rounded up to the nearest 1 mg) of the prior dose level. If supine hypertension or other adverse events persist after the dose has been reduced, dosing in that subject should be discontinued and appropriate alternative therapy and care provided to the subject as determined by the principal investigator.

In Part A, subjects will be administered study drug by qualified study personnel under the supervision of the Investigator. Study personnel will observe and record date and time of dosing and in the event any deviations or incomplete administrations will be noted in the source records.

In Part C, subjects will be administered study drug by qualified study personnel under the supervision of the Investigator on Day 1 and Day 2. On all other dosing days, subjects will record the date and time of their daily dose in a dosing diary. Any dose increases, missed doses, or issues with dosing should be noted in the dosing diary. Site staff will also record any dose increase in the subject's source documents. Subjects are expected to bring the

dosing diary and any empty and/or partially used bottles of study drug to the clinic on their return visits.

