6 STUDY PROCEDURES

6.1 Schedule of Study Procedures

The schedule of study procedures/assessments are summarized in [Table 1](#) for Part A and [Table 2](#) for Part C of the study. Study procedures listed in each row of the table should be performed at the visits designated in each column where an “X” is marked, and as indicated in the footnote, where applicable. Further information related to each study procedure type are described in Section [6.3.3](#).

The calendar day of the first study drug administration is designated as Day 1; subsequent calendar days are Days 2, 3, etc. Note that each part of the study (Parts A and C) has their own unique numbering of calendar days.

Written informed consent must be obtained prior to performing any protocol specific procedures. After providing full informed consent, subjects will undergo a medical screen to determine their eligibility for participation based on the criteria outlined in this protocol. Part C, which is an optional long-term extension study will require subjects to sign a separate informed consent form from that in Part A.

The site should make every effort to perform procedures at the scheduled times, and the actual time should be recorded in the source documents and on the case report forms.

Acceptable deviations from the timing of assessments are as follows:

- Day 8 through Day 29: \pm 3 days
- Day 57 through Day 169: \pm 7 days

Additional safety tests, such as vital signs (BP, heart rate, respiratory rate, and body temperature), physical exams, ECGs, and laboratory safety tests, may be obtained during the course of the study on the basis of newly available data to ensure appropriate safety monitoring.

In Part C, in cases where the subject is unable to return to the clinic for a clinic visit for reasons due to significant physical or geographic limitations, or at the Investigator’s discretion, a protocol-trained nurse may be sent to the subject’s home and the study visit procedures performed in the subject’s home. The only exception to this is for the day 29 visit of Part C which must be done at the research center.

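### Part C allows two dose orders on clinic mornings, and the SAP reports the resulting pre-breakfast blood pressure and standing-duration values under one label with no time-since-dose rule

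*Protocol*

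**What the plan says.** **Dose order.** Protocol Table 2, footnote m says that on the marked visit days "subjects will receive a dose of study medication in the morning after supine blood pressures and the orthostatic standing test has been completed". Further on, for days with travel to the clinic, it says "the subject should take their dose of study medication at home before traveling to the clinic". Nothing ranks the two sentences.

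**Test timing.** Footnote d sets the morning test by meal and clock: "The orthostatic standing test will be performed in the morning before eating breakfast at approximately the same time of day each visit". It fixes the repeat test at 4 to 7 hours after dosing and refers the reader to the visit-day sequence printed below the footnotes. That sequence, with hypothetical times, has the test at 7:30 and then "8:00 am - Dose with TD-9855 and eat breakfast". It shows no travel case.

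**Where subjects are.** Subjects are resident through the morning of Day 2, and under Protocol 5.2 "subjects will be administered study drug by qualified study personnel under the supervision of the Investigator on Day 1 and Day 2". After that, per the synopsis, "Subjects will return on an outpatient basis". Protocol 6.1 lets a nurse carry out a visit at home: "The only exception to this is for the day 29 visit of Part C which must be done at the research center". Footnote m separately has subjects come to the clinic on the day of the last dose, Day 140.

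**Analysis.** SAP 6.2 takes the pre-breakfast Day 1 value as baseline for blood pressure, heart rate and standing duration. SAP 6.3 defines windows in days. SAP 9.2.2 summarizes seated SBP, standing SBP and standing duration by visit at two labelled times, pre-breakfast and pre-lunch. SAP 9.2.3 summarizes supine SBP by visit and names no time of day. SAP 9.3.4 defines a sustained supine elevation from consecutive pre-breakfast and pre-lunch values that can run across visits. Dose times appear only in a listing (SAP 9.3.1).

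**The concern.** The pre-breakfast label reads as if it meant pre-dose, because the Day 1 baseline, Day 2 and the illustrated sequence are all pre-dose. A subject who doses at home and then travels to the clinic fasting also satisfies footnote d, and that morning test is post-dose. The label therefore does not fix the time since dose, and nothing in the SAP restores it.

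Part C is meant to show a sustained pressor response. The repeat standing test is tied to 4 to 7 hours after dosing, so the morning test is the only scheduled standing test that can show standing blood pressure late in the dosing interval. If its timing relative to the dose shifts between Day 2 and later visits, the morning rows and plots of three secondary endpoints combine the effect of repeated dosing with a change in time since dose. The morning supine readings, which bear on supine hypertension, have the same weakness.

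**Working it through.** The plan gives no figure to reproduce on this point. The check sets the texts side by side, counts the readings exposed, and bounds what can be bounded.

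**1. Timing of the morning test under each reading of footnote m**

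| Visit | Setting | Travel sentence is an exception | Sentences conflict |
|---|---|---|---|
| Day 1 (baseline), Day 2 | Resident, dosed by staff | Pre-dose | Pre-dose |
| Days 15, 85 | Clinic, or home with nurse | Post-dose for same-morning travellers, pre-dose at home | Either, by site |
| Day 29 | Research center only | Post-dose for same-morning travellers | Either, by site |
| Day 140 | Clinic per footnote m; home not ruled out by 6.1 | Post-dose for travellers; mixed only if home visits occur | Either, by site |
| Days 8, 22, 57, 113 (supine only) | Telephone day, no travel | Pre-dose | Pre-dose |

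On the exception reading the main problem lies across visits: Day 2 is pre-dose and later clinic visits are not. Mixing within a visit needs home visits, so it can occur at Days 15 and 85, and possibly Day 140, but not at Day 29. On the conflict reading it can occur at any of the four visits.

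**2. Readings exposed.** On-drug standing-test visits after Day 2 are Days 15, 29, 85 and 140: 4 visits × 2 tests = 8 readings per subject. The 4 pre-breakfast readings have no fixed relation to that day's dose. The 4 pre-lunch readings are held to 4 to 7 hours after it.

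**3. Time since dose.** With the illustrated times, a dose at 8:00 and a test at 7:30 next morning gives 23.5 h. With home dosing it is travel plus check-in time, assumed here as 0.5 to 3 h (not in the documents). The difference is 23.5 − 3 = 20.5 h to 23.5 − 0.5 = 23 h.

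**4. Exposure bound.** The protocol recommends at least 7 daily doses per dose level to reach steady state. Assume 7 days (168 h) equals k half-lives, with k from 3 to 5. Then t½ = 168/k, and the steady-state peak-to-trough ratio is at most 2^(24/t½):
- k = 3: t½ = 56 h, ratio 1.35
- k = 4: t½ = 42 h, ratio 1.49
- k = 5: t½ = 33.6 h, ratio 1.64

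**5. Shift in a pooled morning mean.** Let q be the share tested after that day's dose and D the post-dose minus pre-dose difference. The shift is q × D and the added between-subject variance is q(1 − q)D². Neither input is documented. For assumed D of 5, 10 and 15 mm Hg:
- q = 0.5: shift 2.5, 5.0, 7.5 mm Hg; added variance 6.25, 25, 56.25 mm Hg²
- q = 1: shift 5, 10, 15 mm Hg; no added variance, but the row is wholly post-dose against a pre-dose baseline

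**6. Supine chain.** SAP 9.3.4 can count Day 8 pre-breakfast, Day 8 pre-lunch and Day 15 pre-breakfast as three consecutive values. For a travelling subject these fall about 23.5 h, 4 to 7 h and 0.5 to 3 h (assumed) after the last dose.

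**The case against.** The intended order is clearer than footnote m alone suggests. Footnote d points to a sequence that tests before dosing, so the defect is one unreconciled travel sentence. That narrows the problem but does not remove it: a site that follows the travel sentence complies with the protocol and produces post-dose morning values.

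The gap of 20.5 to 23 h counts hours and not drug effect. Dosing is cyclic: 23.5 h after one dose is only 1 to 3.5 h away from 0.5 to 3 h after the next. Part A's primary blood pressure window is 6 to 8 h, later than the assumed travel times, and accumulation flattens the profile. This stands, and it is why no mm Hg harm is claimed.

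The protocol contrasts acute with sustained response, and no endpoint is defined as a trough. Ambulatory or home monitoring over 24 h is scheduled before Days 15, 29 and 85, and Day 2 gives a clean pre-dose standing test after one dose. These partly cover late-interval blood pressure. They do not give a standing test or a standing duration late in the interval after repeated dosing.

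A reader might infer that home and clinic timing mix at every later visit. On the exception reading the documents do not support this, since Day 29 cannot be a home visit and Day 140 is described as a clinic day.

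**Conclusion.** The point holds in a limited form. The plan leaves time since dose inconsistent across visits for the pre-breakfast values of seated SBP, standing SBP and standing duration, and possibly within visits, and the SAP has no rule to separate them. Each later value is still an on-drug versus pre-treatment contrast; what is lost is how long after a dose it applies. Morning supine values are affected in the same way, including the sustained-elevation rule.

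Half of the on-drug standing tests after Day 2 (4 of 8 per subject) are exposed. The effect in mm Hg depends on two quantities the documents do not give. It may be moderate, on the assumption that 7 daily doses span 3 to 5 half-lives.

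Two stronger conclusions are tempting. One is that the week 4 result is compromised. It is not: OHSA question 1 asks about the past week and is completed 4 to 7 hours after dosing. The pre-lunch readings are also unaffected. The other is that an error rate is inflated. It is not: the SAP plans only descriptive summaries. The damage is to interpretation of the morning rows, which is worth correcting because the correction is cheap.

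**What to change.** - **Protocol, Table 2 footnote m:** state which single dose order applies on clinic days. The choice is the sponsor's, because holding the dose until after the test means symptomatic subjects travel undosed.
- **SAP 9.2.2 and 9.3.4, and the supine SBP summary in 9.2.3:** derive hours since last dose. By visit, present morning values taken before that day's dose separately from those taken after it, and show values lacking a usable time as unclassified.

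The data exist. Protocol 5.2 says "subjects will record the date and time of their daily dose in a dosing diary", Protocol 6.1 asks for actual assessment times on the case report form, and SAP 9.3.1 already lists dose date and time. The cost is one derived variable and one clarified footnote. The downside is smaller subsets at each visit, and the pre-dose subset at clinic visits may be very small if sites followed the travel sentence. The footnote change helps only visits still to come; the derived variable also covers data already collected.

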ICH	International Council on Harmonization of Technical Requirements for Registration of Pharmaceuticals for Human Use
IEC	Independent Ethics Committee
IRB	Institutional Review Board
IUD	intra-uterine device
LDH	lactose dehydrogenase
LS	least square
MAO-I	monoamine oxidase inhibitor
MAR	missing at random
MedDRA	Medical Dictionary for Regulatory Activities (MedDRA®)
MSA	multiple system atrophy
NE	norepinephrine

LIST OF ABBREVIATIONS AND DEFINITION OF TERMS

Abbreviation	Description
NET	norepinephrine transporter
nOH	neurogenic orthostatic hypotension
NRI	norepinephrine Reuptake Inhibitor
NYHA	New York Heart Association
OH	Orthostatic Hypotension
OHDAS	Orthostatic Hypotension Daily Activity Scale
OHQ	Orthostatic Hypotension Questionnaire
OHSA	Orthostatic Hypotension Symptom Assessment
PAF	pure autonomic failure
PD	Parkinson's disease
PD	pharmacodynamic(s)
PI	principal investigator
PK	pharmacokinetic(s)
PT	preferred term
QTcF	corrected QT interval
REB	Research Ethics Board
SA	sinus arrhythmia
SAE	serious adverse event
SBP	systolic blood pressure
SERT	serotonin transporter
SOC	system organ class
SOP	standard operating procedure
TEAE	treatment-emergent adverse event
TOEPH	heterogeneous banded Toeplitz structure
WBC	white blood cell count

1 INTRODUCTION

1.1 Background and Rationale

[REDACTED]

[REDACTED]

[REDACTED]

Term	Percentage
Smartphone	~85%
Cloud computing	~90%
Big data	~95%
Machine learning	~98%
Artificial intelligence	~95%

1.2 Nonclinical Profile

A review of the nonclinical profile of TD-9855 can be found in the current version of the TD-9855 Investigator's Brochure (IB).

1.3 Clinical Experience

[REDACTED]

11. **What is the primary purpose of the following statement?**

[REDACTED]

[REDACTED]

© 2013 by the author; licensee MDPI, Basel, Switzerland. This article is an open access article distributed under the terms and conditions of the Creative Commons Attribution license (<http://creativecommons.org/licenses/by/3.0/>).

For more information, contact the Office of the Vice President for Research and Economic Development at [contact] or [contact].

[REDACTED]

A solid black horizontal bar, likely a placeholder or a redacted section of the document.

Entity	Percentage
Alabama	100
Alaska	100
Arizona	100
Arkansas	100
California	100
Colorado	100
Connecticut	100
District of Columbia	100
Florida	100
Georgia	100
Hawaii	100
Idaho	100
Illinois	100
Indiana	100
Iowa	100
Kansas	100
Louisiana	100
Maine	100
Maryland	100
Massachusetts	100
Michigan	100
Minnesota	100
Mississippi	100
Missouri	100
Montana	100
Nebraska	100
Nebraska	100
North Carolina	100
North Dakota	100
Ohio	100
Oklahoma	100
Oregon	100
Pennsylvania	100
Rhode Island	100
South Carolina	100
South Dakota	100
Tennessee	100
Texas	100
Utah	100
Vermont	100
Virginia	100
Washington	100
West Virginia	100
Wisconsin	100
Wyoming	100

1.4 Risks and Benefits

[REDACTED] suggesting that TD-9855 has the potential to provide a novel treatment option for nOH.

While it is not known whether TD-9855 will provide clinical efficacy, this study will provide a number of beneficial services to subjects. These include autonomic evaluations, neurohumoral evaluation and information on new research developments in the field. Subjects will have access to routine autonomic follow up that may improve orthostatic symptoms. They will have symptom rating testing performed that may assist in educational planning.

During the conduct of the TD-9855 clinical development program, the following have been recognized as important potential risks, with none characterized as identified risks associated with the administration of TD 9855:

- Increase in heart rate
- Increase in BP
- Syncope

Possible risks to subjects participating in this study include adverse events associated with other SNRIs, such as nausea, dry mouth, headache, dizziness, somnolence, fatigue, diarrhea, insomnia, vomiting, syncope, seizures, constipation, hyponatremia, hyperhidrosis, urinary retention, and decrease appetite.

Furthermore, subjects may experience adverse effects as a result of study procedures, such as repeated blood sampling and associated procedures.

To help ensure subject safety, subjects will be closely monitored during this study. The study will be conducted in the Clinical and Translational Science Awards Centers (CTSAs) of the respective participating institutions comprising the Autonomic Disorders Consortium whenever possible. When a CTSA is not available, study visits will be conducted in the Investigator's autonomic disorders clinic or appropriately qualified research facility. The schedule of procedures conducted during the open-label out-patient extension requires subjects to return to the clinic on a regular basis during the dosing and follow up periods and participate in telephone based evaluations on a weekly basis. If subjects are unable to return to the clinic as indicated by the schedule of procedures, home visits will be conducted by protocol-trained nurses. If any participant should incur any unexpected and untoward event during the testing procedure, the emergency caregivers (cardiologists, anesthesiologists, social workers, and psychologists) would become available on an immediate basis to provide necessary emergent management.

A summary of known and potential risks to human subjects is provided in the IB in the Summary of Data and Guidance for the Investigator.

